**Figure 1 Study Design**

## 4.2. Treatment Arms and Duration

Eligible patients will receive mepolizumab 100 mg SC every 4 weeks for 28 weeks and will be requested to participate in the study for a maximum of 38 weeks (Visit 0 to the Exit Visit (Visit 10), inclusive as described in [Table 2](#)).

**Table 2** Study phases

Phase	Phase Title	Duration	Description
1	Pre-screening	0 to 2 weeks	At the Pre-screening Visit, details about the study and procedures will be explained through the informed consent process. The Pre-screening Visit (Visit 0) can occur on the same day as the Screening Visit (Visit 1) but must be completed prior to initiating any Visit 1 procedures.
2	Screening / Run-in	1 to 4 weeks	Subjects who meet all the eligibility criteria at Screening, will enter the run-in period for a minimum of 1 week and a maximum of 4 weeks in order to continue to assess the subject's eligibility for the study. Subjects who experience an asthma exacerbation during the run-in period should receive treatment for their exacerbation and remain in the run-in period until the investigator considers that the subject has returned to their baseline asthma status for at least one week. Those subjects that are not eligible to continue in the study at the end of the 4 week run-in period will be deemed run-in failures (see Section 5.4 ).
3	Treatment	32 weeks	At Visit 2 (Week 0) those subjects who successfully complete the run-in period as well as meet the other pre-defined eligibility and continuation to treatment criteria (see Section 5.3 ) will receive mepolizumab 100 mg SC every 4 weeks for a total of 8 doses.  The treatment period will conclude with subjects completing Exit Visit (Visit 10) assessments approximately 4 weeks after the subject was administered their last dose of study treatment at Visit 9.

#### **4.2.1. Exit Interview**

A Single optional Exit Interview to characterize the patient experience of change in asthma will be conducted at the Exit Visit (Visit 10) or Early Withdrawal Visit in a subset of sites and in a subset of patients who consent to participate (See Section 7.3.2.2).

#### **4.3. Type and Number of Subjects**

Approximately 155 subjects will be screened to achieve 120 treated with mepolizumab. Assuming a 15% withdrawal rate, this will result in approximately 100 evaluable subjects completing 32 weeks of mepolizumab treatment.

#### **4.4. Design Justification**

The study is designed to investigate whether subjects not optimally controlled on current omalizumab can be safely and effectively switched to treatment with mepolizumab. Subjects enrolled into the study will already be receiving omalizumab and therefore have previously been identified as suitable for omalizumab treatment according to the product label, and any additional criteria applicable in the participating countries. The dose of omalizumab should previously have been determined by the subject's weight and level of IgE.

Subjects with severe asthma who are not optimally controlled on omalizumab will be identified through the ACQ-5 with a score of  $\geq 1.5$ , at both Visits 1 and 2 respectively and a history of  $\geq 2$  exacerbations in the past 12 months. For those subjects receiving omalizumab for  $\geq 8$  months, at least 1 exacerbation must be while on omalizumab treatment.

The treatment duration of 32 weeks (inclusive of Exit Visit) will enable an adequate time to assess the impact of mepolizumab on ACQ-5, lung function and SGRQ after wash-out of omalizumab, usually 5 half-lives or 4.5 months. In addition, safety, immunogenicity and tolerability endpoints will be assessed during the study.

An open-label single arm design with a direct switch, i.e. the substitution of one biologic with another biologic with no wash-out period, is expected to reflect clinical practice.

#### **4.5. Dose Justification**

The dose selection is based on previous experience from the mepolizumab Phase III program, including two Phase III placebo-controlled studies MEA115588 [Ortega, 2014b] and MEA115575 [Bel, 2014] that demonstrated the safety and efficacy of mepolizumab at a dose of 100 mg SC every 4 weeks.

## 4.6. Benefit: Risk Assessment

Summaries of findings from both clinical and non-clinical studies conducted with mepolizumab (SB-240563) can be found in the Investigator's Brochure. The following section outlines the risk assessment and mitigation strategy for this protocol:

### 4.6.1. Risk Assessment

- Across the mepolizumab development program, chronic dosing of mepolizumab up to 750 mg intravenous (IV) every 4 weeks has been associated with an adverse event (AE) profile similar to placebo (both dosed in addition to standard of care therapy), in the patient populations studied, including mild to moderate asthma and severe refractory asthma.
- The majority of reports of systemic non-allergic and allergic (i.e., hypersensitivity) reactions have been non-serious and resolved without sequelae following minimal supportive care. There have been rare reports of serious reactions. To date, in the phase II and III program in severe asthma there have been no reports of severe life-threatening anaphylaxis related to mepolizumab.
- Anti-drug antibodies (ADA) have been observed infrequently and have not been associated with negative clinical outcomes; there has been no evidence of untoward or persistent neutralizing antibodies (NaB) at any dose.
- Infection rates have been similar across treatment groups. The data to date do not support an association between treatment with mepolizumab and an increased risk of clinically serious opportunistic or parasitic infections.
- Reports of malignancies have been similar between treatment groups in placebo-controlled trials. The known biology of IL-5 and eosinophils suggest that blocking the binding of IL-5 to its receptor with mepolizumab would not likely induce an immuno-suppressive effect that would impair host surveillance against malignancy.
- In previous studies patients on omalizumab and other monoclonal antibodies have been excluded to minimise the risk of confounding factors. Cytochrome P450 enzymes, efflux pumps and protein-binding mechanisms are not involved in the clearance of mepolizumab; furthermore mepolizumab target is specific (cytokine IL-5). The potential for drug-drug interactions with mepolizumab is therefore considered low.

Summaries of findings from both clinical and non-clinical studies conducted with mepolizumab can be found in the IB. The following section ([Table 3](#)) outlines the risk assessment and mitigation strategy for this protocol:

**Table 3 Risk Assessment for mepolizumab**

Potential Risk of Clinical Significance	Summary of Data/Rationale for Risk	Mitigation Strategy
Investigational Product (IP) mepolizumab		
Risk of Systemic Allergic and Non- allergic Reactions, including Anaphylaxis	
Biopharmaceutical products administered subcutaneously may elicit systemic (e.g. hypersensitivity) and local site reactions. Reactions reported to date across the mepolizumab program are summarized in the IB; see 'Special Warnings and Special Precautions for Use' section located in Section 6 titled 'Summary of Data and Guidance for the Investigator'.
	
Daily monitoring of serious adverse events (SAEs) by medical monitor; regular systematic review of adverse event (AE)/SAE data from ongoing studies by a GSK safety review team.
 
Specific case report form (CRF) pages utilized for targeted collection of reactions data.
 
Use of Joint National Institute of Allergy and Infectious Diseases (NIAID)/ Food Allergy and Anaphylaxis Network (FAAN) 2nd Symposium on Anaphylaxis to collect data on reports of anaphylaxis (see Appendix 7)
 
Subjects are to be monitored post-injection for one hour for the first 3 injections, then per institutional guidelines.

Risk of Immunogenicity	
Biopharmaceutical products may elicit anti-drug antibody (ADA) and neutralizing antibody (NaB), which has the potential to modulate pharmacokinetic (PK), pharmacodynamic (PD) or produce adverse reactions. However, humanized and fully human antibodies are less immunogenic than mouse or chimeric monoclonal antibodies.
 
Immunogenicity data reported to date across the mepolizumab development program are summarized in the IB; See 'Clinical Immunogenicity' and a summary of immunogenicity findings in the 'Other Potentially Clinically Relevant Information for the
	
Blood samples are collected in clinical studies for detection of both ADA and NaB
 
See previous risk for mitigation strategy related to clinical safety risks

Potential Risk of Clinical Significance	Summary of Data/Rationale for Risk	Mitigation Strategy
	Investigator' section titled 'Summary of Data and Guidance for the Investigator'.	
Potential risk for adverse cardiovascular (CV) effects	
Mepolizumab binding was restricted to human lymphoid tissues in an immuno-histochemistry tissue binding study suggesting a low likelihood of non-pharmacologic effects on cardiovascular (CV) function.
 
No AEs concerning cardiac conduction or repolarization evident in cynomolgus monkeys at doses at least 10-fold in excess of humans dosed at 10 mg/kg or 750 mg.
 
No clinically relevant trends observed in ECG data in humans.
 
In one study in subjects with severe refractory asthma, cardiac events were reported in similar frequencies across treatment groups with a small numerical increase observed in serious ischemic cardiac events in the mepolizumab-treated groups. However, an integrated safety analysis of all placebo-controlled multiple dose asthma trials showed similar frequency of SAEs reported overall from the cardiac and vascular system organ class (SOC). Additionally, similar findings were observed in other SOCs with thrombotic events (e.g., stroke in the Nervous System SOC).
	
Subjects with uncontrolled, severe or clinically significant cardiovascular disease are excluded from study participation.
 
Daily monitoring of SAEs by medical monitor; regular systematic review of AE/SAE data from ongoing studies by a GSK safety review team.
 
CV monitoring for study includes:
 
ECG monitoring during the trial
 
Use of standardized case report form (CRFs) to collect relevant data on CV as per GSK standard practice.

Potential Risk of Clinical Significance	Summary of Data/Rationale for Risk	Mitigation Strategy
Potential risk for increase in infections- a theoretical concern with biologics	
The pharmacological properties of mepolizumab suggest the risk is low.
 
No evidence of increased incidence of infections in any preclinical studies.
 
Murine data demonstrate that IL-5 antagonism is unlikely to influence cellular or humoral immunity, particularly in response to parasitic infections.
 
No mepolizumab-related effects on lymphocyte Immunophenotyping in monkeys or humans, including T-cell activation, distribution of (cluster of differentiation )CD4/CD8 subtypes or T helper cell (Th1/Th2) cytokine patterns, B-cells, natural killer (NK) cells or <math>\gamma\delta</math>-T-cells.
 
An integrated safety analysis of all placebo-controlled multiple dose asthma trials showed similar reports of infections, including serious and opportunistic, across treatment groups including placebo.
 
Infections reported to date across the mepolizumab development program are summarized in the IB; see 'Special Precautions and Warnings' (for exclusion of subjects with underlying parasitic infections) and 'Undesirable Effects' (for very common infections of nasopharyngitis, upper respiratory tract infection (URTI), rhinitis and bronchitis reported in other patient populations) sections titled 'Summary of Data and Guidance for the Investigator'.
	Daily monitoring of SAEs by the medical monitor; regular systematic review of AE/SAE data from ongoing studies by a GSK safety review team. Standard safety assessments to be conducted as outlined in protocol
Potential risk for increase in malignancies- theoretical concern with biologics.	
Blockage of IL-5 is not associated with generalized immune-suppression or impaired host resistance.
 
Role of IL-5 and eosinophils in tumor surveillance is not fully characterised in the literature.
 
No evidence of defective tumor surveillance in IL-5 or
	Daily monitoring of SAEs by medical monitor; regular systematic review of AE/SAE data from ongoing studies by a GSK safety review team. Standard safety assessments to be conducted as outlined in protocol

Potential Risk of Clinical Significance	Summary of Data/Rationale for Risk	Mitigation Strategy
	
eosinophil-deficient mice.
 
Direct assessment of the carcinogenic potential of long-term IL-5 blockade in rodent models not technically feasible.
 
An integrated safety analysis of all placebo-controlled multiple dose asthma trials showed similar reports of malignancies across treatment groups including placebo.
 
Malignancies reported to date across the mepolizumab development program are summarized in the IB.
	
Potential risk for rebound eosinophilia with associated clinical consequences.	
Early published data with Schering-Plough anti- IL5 mAb suggested potential for rebound eosinophilia and disease exacerbation when treatment was stopped [Kim, 2004; Gevaert, 2006]; however, no standard definition of rebound was used and criteria for reporting were variable.
 
There have been no verbatim reports of 'rebound' from completed clinical trials of subjects with asthma, atopic dermatitis and eosinophilic esophagitis.
 
Furthermore, the data do not support an exaggerated return of symptoms after cessation of treatment.
	
Daily monitoring of SAEs by medical monitor; regular systematic review of AE/SAE data from ongoing studies by a GSK safety review team
 
Standard safety assessments to be conducted as outlined in protocol.

Study Procedures		
Potential risk for injury with phlebotomy	Risks with phlebotomy include bruising, bleeding, infection, nerve damage.	Procedures to be performed by trained personnel (i.e., study nurse)

#### 4.6.2. Benefit Assessment

Data from earlier studies [Haldar 2009; Pavord, 2012] attest to the clinical utility of mepolizumab in the treatment of severe eosinophilic asthma, as do the data from recently completed Phase III studies MEA115575 and MEA115588 [Bel, 2014; Ortega, 2014b].

In this study, benefit considerations for a subject may include:

- Potential benefit of receiving a drug which may have clinical utility in patients with uncontrolled asthma symptoms
- Medical evaluations/assessments associated with study procedures

#### 4.6.3. Overall Benefit: Risk Conclusion

Current data from mepolizumab clinical development have demonstrated its clinical utility in the treatment of eosinophilic asthma. Data from the Phase III asthma programme with mepolizumab demonstrated, compared to placebo, a reduction in asthma exacerbations, improvements in asthma control and quality of life (as measured by the ACQ and SGRQ, respectively), improvements in lung function and a reduction in steroid use in those subjects on chronic OCS treatment.

To date, the safety profile of mepolizumab has been similar to placebo and AEs reported commonly are non-serious and manageable with minimal supportive care. Furthermore, there have been no safety concerns identified or signals observed with mepolizumab that would preclude further investigation in severe asthma.

Taking into account the measures taken to minimize risk to subjects participating in this study, the potential risks identified in association with mepolizumab are justified by the anticipated benefits that may be afforded to a subject with severe asthma. Therefore, the Sponsor considers that the efficacy, safety and tolerability of mepolizumab is justified in study 204471 with a positive benefit/risk ratio.

### 5. SELECTION OF STUDY POPULATION AND WITHDRAWAL CRITERIA

Specific information regarding warnings, precautions, contraindications, adverse events, and other pertinent information on the GSK investigational product or other study treatment that may impact subject eligibility is provided in the IB brochure

Deviations from inclusion and exclusion criteria (see Inclusion Criteria Section 5.1, Exclusion Criteria Section 5.2 and continuation to treatment Section 5.3) are not allowed because they can potentially jeopardize the scientific integrity of the study, regulatory acceptability or subject safety. Therefore, adherence to the criteria as specified in the protocol is essential.

## 5.1. Inclusion Criteria

A subject will be eligible for inclusion in this study only if all of the following criteria apply:

AGE
1. At least 12 years of age at the time of signing the informed consent. [For those countries where local regulations permit enrolment of adults only, subject recruitment will be restricted to those who are $\geq 18$ years of age]
TYPE OF SUBJECT AND DIAGNOSIS INCLUDING DISEASE SEVERITY

2. Asthma: A physician diagnosis of asthma for <math>\geq 2</math> years that meets the National Heart and Lung Institute guidelines [National heart, lung and blood institute (NIH), 2007] or GINA guidelines (GINA, 2015)
 
3. FEV1: Persistent airflow obstruction as indicated by:
 
For subjects <math>\geq 18</math> years of age at Visit 1, a pre-bronchodilator FEV1 <math>< 80\%</math> predicted [Quanjer, 2012] recorded at Visit 1
 
For subjects 12-17 years of age at Visit 1, a pre-bronchodilator FEV1 <math>< 90\%</math> predicted [Quanjer, 2012] recorded at Visit 1
 
OR
 
FEV1/FVC ratio <math>< 0.8</math> recorded at Visit 1
 
4. Eosinophilic asthma: Airway inflammation characterized as eosinophilic in nature as indicated by one of the following:
 
a. A peripheral blood eosinophil count of <math>\geq 300</math> cells/<math>\mu</math>L that is related to asthma demonstrated in the past 12 months prior to Visit 1
 
OR
 
b. A peripheral blood eosinophil count of <math>\geq 150</math> cells/<math>\mu</math>L at Visit 1 that is related to asthma.
 
5. Inhaled Corticosteroid: A well-documented requirement for regular treatment with high-dose inhaled corticosteroid (ICS) in the 12 months prior to Visit 1 with or without maintenance oral corticosteroids (OCS).
 
For 18 years of age and older:      ICS dose must be <math>\geq 880</math> mcg/day fluticasone propionate (FP) (ex-actuator) or equivalent daily      For ICS/LABA combination preparations, the highest approved maintenance dose in the local country will meet this ICS criterion.

TYPE OF SUBJECT AND DIAGNOSIS INCLUDING DISEASE SEVERITY	
	For subjects 12-17 years of age at Visit 1: ICS dose must be $\geq 440$ mcg/day fluticasone propionate (FP) (ex-actuator) or equivalent daily
	For ICS/LABA combination preparations, the highest approved maintenance dose in the local country will meet this ICS criterion.
6.	Controller Medication: Current treatment with an additional controller medication, besides ICS, for at least 3 months or a documented failure in the past 12 months of an additional controller medication for at least 3 successive months. [e.g., long-acting beta-2-agonist (LABA), leukotriene receptor antagonist (LTRA), long-acting anticholinergic (tiotropium bromide), or theophylline.]
7.	Asthma symptoms not optimally controlled: An ACQ-5 score of $\geq 1.5$ recorded at Visit 1.
8.	Omalizumab Treatment: Receiving omalizumab, based on weight and IgE levels, for at least the 4 months prior to Visit 1.
9.	Exacerbation history: Previously confirmed history of two or more exacerbations requiring treatment with systemic corticosteroids (intramuscular, intravenous, or oral) in the 12 months prior to Visit 1 despite the use of high-dose ICS. For subjects receiving omalizumab for $\geq 8$ months, at least one exacerbation must have occurred while on omalizumab treatment. For subjects receiving maintenance oral corticosteroids, the corticosteroid treatment for the exacerbations must have been a two-fold dose increase or greater.

SEX
10. Male or eligible Female
Females:
a. Non-reproductive potential defined as:

 
• Pre-menopausal females with one of the following:           
 
• Documented tubal ligation
 
• Documented hysteroscopic tubal occlusion procedure with follow-up confirmation of bilateral tubal occlusion
 
• Hysterectomy
 
• Documented Bilateral Oophorectomy
 
 
 
• Postmenopausal defined as 12 months of spontaneous amenorrhea [in questionable cases a blood sample with simultaneous follicle stimulating hormone (FSH) and estradiol levels consistent with menopause (refer to laboratory reference ranges for confirmatory levels)]. Females on hormone
 

## SEX

replacement therapy (HRT) and whose menopausal status is in doubt will be required to use one of the highly effective contraception methods if they wish to continue their HRT during the study. Otherwise, they must discontinue HRT to allow confirmation of post-menopausal status prior to study enrolment.

b. Reproductive potential and agrees to follow one of the options listed in the Modified List of Highly Effective Methods for Avoiding Pregnancy in Females of Reproductive Potential (FRP) (see [Appendix 3](#)) from 30 days prior to the first dose of study medication and until at least five terminal half-lives OR until any continuing pharmacologic effect has ended, whichever is longer, after the last dose of study medication and completion of the Exit visit/Early Withdrawal visit.

The investigator is responsible for ensuring that subjects understand how to properly use these methods of contraception.

## INFORMED CONSENT

11. Capable of giving signed informed consent which includes compliance with the requirements and restrictions listed in the consent form and in this protocol.

## 5.2. Exclusion Criteria

### CONCURRENT CONDITIONS/MEDICAL HISTORY (INCLUDES LIVER FUNCTION AND QTc INTERVAL)

- Concurrent Respiratory Disease:** Presence of a known pre-existing, clinically important lung condition other than asthma. This includes current infection, bronchiectasis, pulmonary fibrosis, bronchopulmonary aspergillosis, or diagnoses of emphysema or chronic bronchitis (chronic obstructive pulmonary disease other than asthma) or a history of lung cancer.
- Malignancy:** A current malignancy or previous history of cancer in remission for less than 12 months prior to screening (subjects that had localized carcinoma of the skin which was resected for cure will not be excluded).
- Liver disease:** Subjects must not be enrolled in the study if :

At screening (Visit 1) ALT >2xULN; and bilirubin >1.5xULN (isolated bilirubin >1.5xULN is acceptable if bilirubin is fractionated and direct bilirubin <35%)

Current active liver or biliary disease (with the exception of Gilbert's syndrome or asymptomatic gallstones or otherwise stable chronic liver disease per investigator assessment).

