**CONCURRENT CONDITIONS/MEDICAL HISTORY (INCLUDES LIVER FUNCTION AND QTc INTERVAL)**

or persistent jaundice, or cirrhosis

4. **Hepatitis status:** Diagnosis of chronic hepatitis B, as evidenced by positive Hepatitis B surface antigen (HBsAg) at Visit 1. Chronic stable hepatitis C (e.g., positive hepatitis C antibody test result at screening (Visit 1) or within 3 months prior to first dose of study treatment) are acceptable if subject otherwise meets entry criteria.

5. **Cardiovascular:** Subjects who have severe or clinically significant cardiovascular disease uncontrolled with standard treatment. Including but not limited to:

- a. known ejection fraction of <30% **OR**
- b. severe heart failure meeting New York Heart Association Class IV (see [Appendix 4](#)) classification **OR**
- c. hospitalised in the 12 months prior to Visit 1 for severe heart failure meeting New York Heart Association Class III (see [Appendix 4](#))  
**OR**
- d. angina diagnosed less than 3 months prior to Visit 1 or at Visit 1

6. **Subjects with QTc > 450 msec or QTc > 480 msec in subjects with Bundle Branch Block at screening Visit 1**

NOTES:

- The QTc is the QT interval corrected for heart rate according to Bazett's formula (QTcB), Fridericia's formula (QTcF), and/or another method, machine-read or manually over-read.
- The specific formula that will be used to determine eligibility and discontinuation for an individual subject should be determined prior to initiation of the study. In other words, several different formulae cannot be used to calculate the QTc for an individual subject and then the lowest QTc value used to include or discontinue the subject from the trial.
- For purposes of data analysis, QTcB, QTcF, another QT correction formula, or a composite of available values of QTc will be used as specified in the Reporting and Analysis Plan (RAP).

7. **Other Concurrent Medical Conditions:** Subjects who have known, pre-existing, clinically significant endocrine, autoimmune, metabolic, neurological, renal, gastrointestinal, hepatic, haematological or any other system abnormalities that are uncontrolled with standard treatment.

8. **Eosinophilic Diseases:** Subjects with other conditions that could lead to elevated eosinophils such as Hypereosinophilic Syndromes, including Churg-Strauss Syndrome (Eosinophilic Granulomatosis with Polyangiitis; EGPA), or Eosinophilic Esophagitis.

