**5.3. Continuation to Treatment Criteria**

At Visit 2, those subjects who fulfil the inclusion/exclusion criteria and who meet the continuation to treatment criteria will commence the study treatment phase until the target of approximately 120 treated subjects is reached.

In order to receive study treatment subjects must have completed the run-in period and must have fulfilled all inclusion and exclusion criteria described in Section 5.1 and Section 5.2. In addition to the following:

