### 5.5.3.1. Study Treatment Restart or Rechallenge

Study treatment restart or rechallenge after liver chemistry stopping criteria are met by any subject participating in this study is not allowed.

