## 7.1. Time and Events Table

Procedures	Pre-screen 	Screen Run-in	Treatment (visit window is $\pm 7$ days)									Exit Visit/ Early withdrawal Visit 
			0	1	2	3	4	5	6	7	8	
Visit	0	1										10
Week	-6 to -4	-4 to -1	0	4	8	12	16	20	24	28		4 weeks post last dose $\pm 7$ days
Informed Consent 	x											
Subject Demography	x											
Medical History		x										
Asthma History (including triggers)	x	x										
Therapy History 		x										
Smoking History		x										
Cardiovascular History/Risk Factors		x										
Inclusion/Exclusion Criteria		x										
Continuation to treatment Criteria			x									
Efficacy Assessments 												
ACQ-5		x	x	x	x	x	x	x	x	x	x	x
Exacerbation review	x	x	x	x	x	x	x	x	x	x	x	x
Spirometry including pre- and post bronchodilator FEV 1 , FVC 		x	x			x			x			x
Health Outcome Assessments 												
SGRQ			x			x			x		x	x

Procedures	Pre-screen 	Screen Run-in	Treatment (visit window is $\pm 7$ days)									Exit Visit/ Early withdrawal Visit 
			0	1	2	3	4	5	6	7	8	
Visit	0	1	2	3	4	5	6	7	8	9	10	
Week	-6 to -4	-4 to -1	0	4	8	12	16	20	24	28	4 weeks post last dose $\pm 7$ days	
Clinician & Subject rated response to therapy					x		x		x			x
Treatment Satisfaction with Medication Questionnaire (TSQM-9)		x										x
Exit Interview 												x
Safety Assessments												
Concomitant Medication	x	x	x	x	x	x	x	x	x	x	x	
Physical Examination, including nasal exam		x										x
Vital Signs		x	x	x	x	x	x	x	x	x	x	
12 lead ECG		x				x						x
Adverse Events		x	x	x	x	x	x	x	x	x	x	
Serious Adverse Events	x	x	x	x	x	x	x	x	x	x	x	
Laboratory Assessments												
Haematology with differential		x	x	x	x	x	x	x	x	x	x	
Clinical Chemistry (incl. LFT)		x	x	x	x	x			x			x
Parasitic Screening 		x										
Pharmacogenetic sample 							x					
Pregnancy test 		U	U	U	U	U	U	U	U	U	U	U
HBsAg and hepatitis C antibody 		x										
Immunogenicity sample			x			x				x		x
Biomarker sample		x	x		x							x

Procedures	Pre-screen 	Screen Run-in	Treatment (visit window is $\pm 7$ days)									Exit Visit/ Early withdrawal Visit 
Visit	0	1	2	3	4	5	6	7	8	9	10	
Week	-6 to -4	-4 to -1	0	4	8	12	16	20	24	28	4 weeks post last dose $\pm 7$ days	
Investigational product (Mepolizumab) and rescue medication												

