### Liver chemistry stopping criteria and required follow up assessments

Liver Chemistry Stopping Criteria - Liver Stopping Event	
ALT-absolute	ALT $\geq$ 8xULN
ALT Increase	ALT $\geq$ 5xULN but $<8$ xULN persists for $\geq 2$ weeks
	ALT $\geq$ 3xULN but $<5$ xULN persists for $\geq 4$ weeks
Bilirubin 	ALT $\geq$ 3xULN and bilirubin $\geq$ 2xULN ( $>35\%$ direct bilirubin)
INR 	ALT $\geq$ 3xULN and INR $>1.5$ , if INR measured
Cannot Monitor	ALT $\geq$ 5xULN but $<8$ xULN and cannot be monitored weekly for $\geq 2$ weeks ALT $\geq$ 3xULN but $<5$ xULN and cannot be monitored weekly for $\geq 4$ weeks
Symptomatic 	ALT $\geq$ 3xULN associated with symptoms (new or worsening) believed to be related to liver injury or hypersensitivity

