
ALT <math>\geq</math> 5xULN and <math><</math> 8xULN and bilirubin <math><</math> 2xULN without symptoms believed to be related to liver injury or hypersensitivity, and who can be monitored weekly for 2 weeks.
 
OR
 
ALT <math>\geq</math> 3xULN and <math><</math> 5xULN and bilirubin <math><</math> 2xULN without symptoms believed to be related to liver injury or hypersensitivity, and who can be monitored weekly for 4 weeks.
	
 
• Notify the GSK medical monitor within 24 hours of learning of the abnormality to discuss subject safety.
 
• Subject can continue study treatment
 
• Subject must return weekly for repeat liver chemistries (ALT, AST, alkaline phosphatase, bilirubin) until they resolve, stabilise or return to within baseline
 
• If at any time subject meets the liver chemistry stopping criteria, proceed as described above
 
• If ALT decreases from ALT <math>\geq</math> 5xULN and <math><</math> 8xULN to <math>\geq</math> 3xULN but <math><</math> 5xULN, continue to monitor liver chemistries weekly.
 
• If, after 4 weeks of monitoring, ALT <math><</math> 3xULN and bilirubin <math><</math> 2xULN, monitor subjects twice monthly until liver chemistries normalize or return to within baseline.
 

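### Exclusion criterion 3 joins its ALT and bilirubin limits with 'and': read literally, it does not exclude raised ALT with normal bilirubin, and no other entry criterion sets an ALT limit

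*Protocol*

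**What the plan says.** Under a lead-in listing when a subject must not be enrolled, exclusion criterion 3 in Protocol Section 5.2 gives the laboratory line "At screening (Visit 1) ALT >2xULN; and bilirubin >1.5xULN (isolated bilirubin >1.5xULN is acceptable if bilirubin is fractionated and direct bilirubin <35" (per cent). A separate line under the same lead-in covers "Current active liver or biliary disease", with exceptions that include stable chronic liver disease as assessed by the investigator.

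Criterion 4 excludes subjects positive for hepatitis B surface antigen. Subjects with chronic stable hepatitis C "are acceptable if subject otherwise meets entry criteria".

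These criteria decide who is dosed. Section 5.3 says that subjects "must have fulfilled all inclusion and exclusion criteria described in Section 5.1 and Section 5.2" before treatment, and the opening of Section 5 allows no deviations.

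Once a subject is on treatment, Appendix 5 (Section 12.5) sets the ALT rules. One of its stopping criteria is "ALT $\geq$ 3xULN but $<5$ xULN persists for $\geq 4$ weeks". Section 5.5.3.1 adds: "Study treatment restart or rechallenge after liver chemistry stopping criteria are met by any subject participating in this study is not allowed".

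**The concern.** The connector and the bracketed exception do not fit together. If both values must be raised to exclude, an isolated bilirubin rise never excludes anyone, so there is nothing for the exception to excuse.

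The literal reading is not far-fetched. Where Section 5 means alternatives it generally says so (inclusion criteria 3 and 4, exclusion criteria 5 and 6). Where these documents join ALT and bilirubin with *and*, they mean both: Appendix 5, the liver item of the SAE definition (Section 12.7.2) and the laboratory flag in SAP Section 10.8.1.

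Two things are at stake. First, a subject with ALT 2.5xULN and normal bilirubin could fail screening at one site and be eligible at another, across the nine countries listed in SAP Section 10.9.1. The text does not say whether enrolling that subject is a deviation, although SAP Section 4.1 summarises and lists all inclusion and exclusion deviations. Second, a subject with a higher stable ALT could give up omalizumab, start mepolizumab and then be stopped for a value already known at screening.

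**Working it through.** The plan gives no figure to reproduce. The check is logical.

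**Step 1: what each reading excludes.** Three conditions come from the laboratory line:
- A: ALT >2xULN at Visit 1.
- B: bilirubin >1.5xULN at Visit 1.
- D: bilirubin is fractionated and the direct share is below 35%.

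The exception E applies when B and D hold and A does not. The candidate readings are:
- Literal: (A and B) and not E.
- List (each limit alone): (A or B) and not E.
- Bilirubin only: B and not E, where ALT only decides whether the bilirubin rise is isolated.

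| A | B | D | Literal | List | Bilirubin only |
|---|---|---|---|---|---|
| no | no | no | admit | admit | admit |
| no | no | yes | admit | admit | admit |
| no | yes | no | admit | exclude | exclude |
| no | yes | yes | admit | admit | admit |
| yes | no | no | admit | exclude | admit |
| yes | no | yes | admit | exclude | admit |
| yes | yes | no | exclude | exclude | exclude |
| yes | yes | yes | exclude | exclude | exclude |

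Deleting the exception changes 0 of 8 rows under the literal reading. Under either of the other two it changes 1 of 8, the row where only bilirubin is raised and the direct share is below 35%. That is exactly the case the exception describes.

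The literal and list readings differ in 3 of 8 rows: one with isolated bilirubin that does not qualify for the exception, and two with ALT raised alone. The exception settles the first. It does not settle the two ALT rows, because the bilirubin-only reading also gives it a function.

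**Step 2: is there another ALT limit at entry?**
- Inclusion criteria (Section 5.1): none.
- Exclusion 3, liver disease line: judgement, no value.
- Exclusion 4: serology, no ALT value; stable hepatitis C is allowed.
- Exclusion 7: hepatic abnormality uncontrolled with standard treatment; judgement, no value.
- Start-treatment criteria (Section 5.3): ACQ-5, exacerbation, maintenance therapy and last omalizumab dose; no liver test.

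ALT thresholds elsewhere are stopping or monitoring rules (Appendix 5), an SAE definition (Section 12.7.2) or a laboratory flag (SAP Section 10.8.1). None is an entry limit.

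**Step 3: what follows for a subject admitted on ALT alone.** Assume a stable elevation, normal bilirubin and no symptoms. Appendix 5 gives:
- ALT >2 to <3xULN: no stopping or monitoring rule applies.
- ALT 3 to <5xULN: stop once it has persisted 4 weeks.
- ALT 5 to <8xULN: stop once it has persisted 2 weeks.
- ALT 8xULN or more: stop.

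None of these three stopping criteria exempts a raised baseline. Baseline does appear in the monitoring rule for the 3 to <8xULN range ("Subject must return weekly for repeat liver chemistries (ALT, AST, alkaline phosphatase, bilirubin) until they resolve, stabilise or return to within baseline"), but that governs how long repeats continue, not whether treatment stops. The longest persistence required is 4 weeks, against dosing from Week 0 to Week 28, so a stable ALT of at least 3xULN could meet a rule early in the course.

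**The case against.** The strongest reply is that the line largely corrects itself. A semicolon before *and*, under a lead-in that introduces exclusions, looks like a list separator. A reading that makes the exception pointless gives a careful reader reason to reject it. Many sites would already read *or*, and no misreading is shown. Harm also needs a chain of conditions: a site applies the literal text; ALT is at least 3xULN and stays there; and the investigator sees neither active liver disease nor an uncontrolled hepatic abnormality. When Appendix 5 then stops treatment, the safety rule is working as designed.

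Most of this stands, and it keeps the point small. It does not remove it, because the literal reading matches how the documents use *and* elsewhere and nothing else in the entry criteria supplies an ALT limit.

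A reader might infer more than the documents support:

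- **That the exception proves ALT must exclude alone.** It concerns isolated bilirubin only. The ALT part rests on reading the connector as a list separator, which is the natural reading but not a proof.
- **That the liver disease line is also left hanging for want of a connector.** It is a separate line under the same lead-in and reads as an exclusion of its own.
- **That silence elsewhere confirms a gap.** The per-protocol exclusions in SAP Section 10.1.1 concern effects on efficacy, so a liver safety limit would not be expected there. The absence of an amendment entry is not evidence either.
- **That the number of doses lost can be bounded, for example at no more than 3 of 8 given.** The documents do not say from which sample persistence is counted, and visits may move by 7 days. Counting from the Week 4 visit, that visit can fall on day 28 + 7 = 35 and Week 8 on day 56 - 7 = 49. The gap is 14 days, short of the 28 needed for ALT 3 to <5xULN. If weekly repeats had ended because values stabilised, the next scheduled chemistry is at Week 12. If that result came back after dosing, doses at Weeks 0, 4, 8 and 12 would have been given, which is 4.

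**Conclusion.** The point holds as a minor drafting inconsistency in an operative safety criterion. As written, the laboratory line excludes only when both values are raised, makes its own exception redundant and sets no effective limit on ALT alone. Even 8xULN with normal bilirubin passes this line at screening, although the same value on treatment is a stopping event. The probable intent is that each limit excludes alone.

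The number of subjects affected is not in the documents and cannot be derived from them. Early stopping is a possibility that depends on a literal-reading site and a stable elevation of at least 3xULN; no number of lost doses should be attached to it. Sample size and the primary analysis are unaffected.

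**What to change.** Replace the connector with OR, so that the laboratory line gives two separate exclusions at Visit 1: ALT >2xULN; OR bilirubin >1.5xULN. Keep the existing bracketed exception attached to the bilirubin limit. The thresholds, the exception and the liver disease line stay as they are. In the table above this excludes raised ALT alone and non-qualifying isolated bilirubin, and leaves the exception with exactly the one case it describes.

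The cost is one amendment line or site clarification, and possibly a few more screen failures at any site that had applied the literal wording.
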